5.0 TREATMENT PLAN

This is a single-arm, open label, phase II trial of single-agent ofatumumab.

Patients will receive ofatumumab 300 mg dose 1, then 1000 mg weekly for 7 additional weekly doses (8 doses). All doses will be administered at MDACC. Allopurinol 300 mg PO daily for the first 7 days of course 1 is recommended for tumor lysis prophylaxis.

There are no required prophylactic antibiotics. Herpes virus and PCP prophylaxis may be given at the discretion of the treating physician but is recommended for patients with recent or concurrent corticosteroid use.

Growth factors (neutrophil, erythrocyte, platelet) may be used at the discretion of the treating physician, if clinically indicated.

Pre-medication for each ofatumumab infusion must be given within 30 minutes to 2 hours prior to the infusion:

Table 1. Pre-medication Requirements prior to Ofatumumab Infusions

Infusion #	Acetaminophen (po) or equivalent	Antihistamine (IV or po) diphenhydramine or equivalent	Glucocorticoid (IV) prednisolone or equivalent
1 st	1000 mg	50 mg	50 mg
2 nd	1000 mg	50 mg	50 mg
3 rd -N th	1000 mg	50 mg	0 – 50 mg ¹

1. If the 2nd infusion has been completed without the subject experiencing any grade = 3 AEs, pre-medication with corticosteroid may be reduced or omitted before the 3rd to Nth infusion at the discretion of the treating physician.

First Infusion of 300 mg ofatumumab

The first dose administered of ofatumumab will be 300 mg to minimize infusion reactions. The initial rate of the first infusion of **300 mg** ofatumumab (0.3mg/ml) should be 12mL/h. If no infusion reactions occur the infusion rate can be increased every 30 minutes, to a maximum of 200 mL/h, according to Table 2.

Table 2. Infusion rate at 1st Ofatumumab Infusion

Time	mL/hour
0 – 30 minutes	12
31 – 60 minutes	25
61 – 90 minutes	50
91 – 120 minutes	100
121 – 150+minutes	200

If an infusion reaction develops, the infusion should be temporarily slowed or interrupted. Upon restart, the infusion rate should be half of the infusion rate at the time the infusion was paused. If, however, the infusion rate was 12 mL/hour before the pause, the infusion should be restarted at 12 mL/hour. Hereafter, the infusion rate may be increased according to the judgment of the investigator, in the manner described in this section.

Subsequent infusion of full dose (1000 mg) ofatumumab

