7.0 EVALUATION DURING STUDY

- 7.1 Monitoring during treatment will consist of weekly (\pm 3 days) blood counts and chemistries (through C1D50), then every 3 months (\pm 2 weeks) during follow-up until alternative treatment for CLL/SLL or death, whichever occurs first. A physician will see patients at least monthly (\pm 5 days) during treatment. A mid-level provider may evaluate patients weekly (\pm 2 days) during treatment (8 weeks) when not seen by the physician.
- 7.2 Follow-up visits will include PE with vital signs, interval history, toxicity/adverse event assessment, CBC with differential, and SMA12. Bone marrow examinations (aspirate, biopsy, and MRD evaluation) will be done at response

assessment (at least 2 months after last dose of ofatumumab) to confirm complete remission, then annually.

- 7.3 Patients will be followed at MDACC for all visits including follow-up, response assessment 3 months after the last ofatumumab dose, and at least annually. Patients will be considered off study when they start alternative treatment for their CLL.
- 7.4 For patients who are HBsAg⁻, HBcAb⁺, HBsAb^{+/-}, and HBV DNA⁻ on enrollment and who proceeded with treatment, HBV DNA PCR testing will be done every 2 months while on treatment, then every 3 months during follow-up for 6 months. Consult with a physician experienced in care and management of subjects with hepatitis B to manage/treat subjects who are anti-HBc positive. Initiate anti-viral therapy if required. If a subject's HBV DNA becomes positive during the study, notify the GSK medical monitor. For subjects who have not completed planned ofatumumab therapy, discuss with the medical monitor the risks and benefits of continuing or discontinuing ofatumumab before appropriate treatment decisions are made for that individual subject.
- 7.5 Information regarding concomitant medications will not be collected for patients on this study. This information is routinely collected and recorded as part of the patient's electronic record. If there is a need to refer to this, it will be available.

The schedule of events is detailed in Table 4.

Table 4. Schedule of Events

Test and Evaluations	Screening Visit Day ≤ -21	C1 D1	C1 D8	C1 D15	C1 D22	C1 D29	C1 D36	C1 D43	C1 D50 (EOT)	C1 D140	FU Q3 MO	ANNUAL FU
Informed consent	X											
Medical history	X											
Interval history, including adverse events and toxicity		X	X ^a	X ^b	X ^c	X ^c						
PE including VS	X	X	X ^a	X ^b	X ^c	X ^c						
Pregnancy test	X											

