8.1 ADVERSE EVENT DOCUMENTATION

Adverse events will be documented in the medical record and entered into the case report form (CRF) according to the Leukemia –Specific Adverse Event Recording and Reporting Guidelines (Appendix E). PDMS/Core will be used as the CRF report form for this protocol. The Investigator or physician designee is responsible for verifying and providing source documentation for all adverse events and assigning the attribution for each event for all subjects enrolled on the trial. The Investigator will sign and date the PDMS CRF toxicity pages for each patient at the completion of each course. Following signature, the CRF will be used as source documentation for the adverse events attribution.

Table 6. 2008 IWCLL Grading for Hematological Toxicity

Grade	Decrease in PLT* or HGB** (nadir) from pretreatment value, %	Absolute neutrophil count (ANC)/ μ l*** (nadir)
0	$\leq 10\%$	≥ 2000
1	11 – 24%	$\geq 1500 - < 2000$
2	25 – 49%	$\geq 1000 - < 1500$
3	50 – 74%	$\geq 500 - < 1000$
4	$\geq 75\%$	< 500

Death occurring as a result of toxicity at any level of decrease from pretreatment will be recorded as grade 5.

* PLT counts must be below normal levels for grades 1-4. If, at any level of decrease, the PLT count is $< 20K/\mu\text{L}$, this will be considered grade 4 toxicity, unless there was severe or life-threatening low initial PLT count ($< 20K/\mu\text{L}$) pretreatment, in which case the patient is not evaluable for toxicity referable to PLT count.

** HGB levels must be below normal levels for grades 1-4. Baseline and subsequent HGB determinations must be performed before any given transfusions.

*** If the absolute neutrophil count (ANC) reaches $<1000/\mu\text{L}$, it should be judged to be grade 3 toxicity. If the ANC was $<1000/\mu\text{L}$ before therapy, the patient is not evaluable for toxicity referable to the ANC.

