10.0 STATISTICAL CONSIDERATIONS

This is a phase II, open label, single-arm study. Sample size calculation will be based on the CR rate. The objective is to demonstrate a 20% CR rate for patients treated with single-agent ofatumumab. A CR rate of 9% was achieved in a previous phase II clinical trial with single-agent rituximab in a similar patient population. Simon's two-stage MinMax design will be used to assess efficacy in this study. In particular, a sample size of 44 is chosen to differentiate between a good response rate of 20% and a poor response rate of 9% at the significance level of 0.10 with 80% power. In particular, 25 patients will be enrolled at the first stage. If there is 1 or fewer responders among 25, the trial will be terminated due to lack of efficacy; otherwise an additional 19 patients will be treated resulting in a total of 44 patients. If there are 6 or fewer responses among 44 patients, the treatment will be concluded ineffective. The probability of early termination due to futility is 0.33.

The probability of toxicity will be monitored based on a beta-binomial model, assuming a priori that $p = \text{Prob}(\text{toxicity}) \sim \text{beta}(1, 1)$. The trial will be terminated if $\text{Prob}(p > .15 | \text{data}) \geq .9$. This rule will stop the trial if $[\#\text{patients with toxicity}] / [\#\text{patients evaluated}] \geq 3/7, 4/12, 5/17, 6/22, 7/27, 8/32, 9/37, \text{ or } 10/42$. The operating characteristics for toxicity are summarized in Table 7.

Table 7. Operating characteristics based on 1000 simulation study

true Prob(tox)	Pr(stop)	Median # Pts (25%, 75%)
0.05	0.004	44 (44, 44)
0.10	0.07	44 (44, 44)
0.15	0.25	44 (44, 44)
0.20	0.49	44 (12, 44)
0.30	0.89	12 (7, 22)
0.40	0.99	7 (7, 12)

Toxicity events, for purposes of safety monitoring, will be defined as ofatumumab-related grade ≥ 4 toxicity by CTCAE V 4.0 that persist longer than 1 week despite holding drug and/or dose reduction.

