- **The MDACC "Internal SAE Report Form for Prompt Reporting" will be used for reporting to MDACC IND Office.**

- Serious adverse events will be captured from the time the patient signs consent until 30 days after the last dose of drug. Serious adverse events must be followed until clinical recovery is complete and laboratory tests have returned to baseline, progression of the event has stabilized, or there has been acceptable resolution of the event.
- Additionally, any serious adverse events that occur after the 30 day time period that are related to the study treatment must be reported to MDACC IND Office. This may include the development of a secondary malignancy.

Reporting to FDA:

- Serious adverse events will be forwarded to FDA by the IND Sponsor (Safety Project Manager MDACC IND Office) according to 21 CFR 312.32.

It is the responsibility of the PI and the research team to ensure serious adverse events are reported according to the Code of Federal Regulations, Good Clinical Practices, the protocol guidelines, the sponsor's guidelines, and Institutional Review Board policy.

All serious adverse events will also be forwarded to GSK according to their guidelines.

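### Does the toxicity stopping rule fail because Section 10 does not say when a patient counts as evaluated?

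*Combined protocol and SAP*

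**What the plan says.** Section 10.0 states that "The probability of toxicity will be monitored based on a beta-binomial model" with a beta(1, 1) prior. The trial stops if the posterior probability that the toxicity rate exceeds .15 is at least .9. The rule is then written as counts of patients with toxicity over patients evaluated: "3/7, 4/12, 5/17, 6/22, 7/27, 8/32, 9/37", and finally 10/42. A qualifying event is an ofatumumab-related toxicity of grade 4 or higher "that persist longer than 1 week despite holding drug and/or dose reduction". Table 7 gives the chance of stopping and the median number of patients, with quartiles, from 1000 simulated trials.

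Other sections bear on timing, but none is tied to the rule:

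- Section 5.0 and Table 4 put the eight doses on days 1 to 50.
- Table 4 in Section 7.0 schedules "Interval history, including adverse events and toxicity" at each weekly treatment visit.
- Section 8.1 says "The Investigator will sign and date the PDMS CRF toxicity pages for each patient at the completion of each course".
- Section 13.0 says "Serious adverse events will be captured from the time the patient signs consent until 30 days after the last dose of drug".

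No accrual rate is given.

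**The concern.** The denominator decides whether the trial stops, and the plan does not define entry to it. An event that starts at the day-50 dose and lasts more than 7 days is confirmed at about day 58. At any look, some treated patients may therefore have an open outcome. They could be left out until complete, counted as event-free in the meantime, or counted early only if they have an event.

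The boundaries are tight enough for this to matter: two events in seven continues and three in seven stops. If patients were counted before their outcome could be known, the rule would be weaker just where it is meant to protect. If enrolment runs on while outcomes are pending, more patients would be treated before a stop than the medians of 7 and 12 in Table 7 suggest. This is the trial's only quantitative safety rule, so the question is a fair one.

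**Working it through.** **1. Boundaries.** Inputs, all from Section 10: beta(1, 1) prior, limit .15, cut-off .9. With x events in n patients the posterior is Beta(1 + x, 1 + n − x), and

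Pr(p > .15 | x, n) = Pr(Binomial(n + 1, .15) ≤ x).

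- 3/7 gives .979; 2/7 gives .895.
- 4/12 gives .966; 3/12 gives .882.
- 10/42 gives .951; 9/42 gives .899.

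At each of the eight listed counts, the printed number is the smallest that reaches .9.

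**2. Table 7 under the ordinary reading.** Take patients in enrolment order, each with a known outcome, and look only at n = 7, 12, …, 42. Carry the binomial distribution of x forward one patient at a time and remove the mass at or above the boundary at each look.

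| True rate | Exact Pr(stop) | Table 7 |
|---|---|---|
| .05 | .006 | .004 |
| .10 | .060 | .07 |
| .15 | .229 | .25 |
| .20 | .501 | .49 |
| .30 | .912 | .89 |
| .40 | .995 | .99 |

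The largest gaps, at .15 and .30, are compatible with 1000 simulated trials and rounding (two-sided p .24 and .07). The result does not depend on the length of the window, because only complete outcomes enter.

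**3. The patient-number column.** The same recursion gives the cumulative chance of stopping by number evaluated.

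- True rate .30: .353 by 7, .546 by 12, .755 by 22. Median 12, quartiles 7 and 22, as printed.
- True rate .40: .580 by 7, .797 by 12. Median 7, quartiles 7 and 12, as printed.
- True rate .20: .243 by 12 and .501 by 42, giving 42 (17, 44) against the printed 44 (12, 44). Both differences sit on a quantile boundary, where 1000 runs can fall either way.

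The column is therefore reproduced as patients evaluated at stopping, with no assumption about enrolment.

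**4. Other ways of counting.** These need assumptions the documents do not supply: 2 patients a month, random arrivals, onset uniform over days 1 to 50, confirmation 8 days after onset, event-free patients complete 57 days after dose 1, no enrolment pause, the efficacy futility stop ignored. The looks and boundaries are unchanged.

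| Counting | .15 | .20 | .30 | .40 |
|---|---|---|---|---|
| Enrolment order, outcome known (exact) | .229 | .501 | .912 | .995 |
| Events counted once confirmed | .279 | .558 | .932 | .997 |
| Everyone counted from one week after dose 1 | .151 | .389 | .856 | .989 |

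Over 1 to 4 patients a month, with onset uniform or confined to week 1, the second row runs from .254 to .420 at .15 and from .530 to .694 at .20. The third runs from .115 to .191 and from .330 to .452.

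**5. Patients treated.** With enrolment-order counting and no pause, the median (quartiles) treated at 2 a month is 17 (12, 28) at true rate .30 and 13 (10, 17) at .40. Over 1 to 4 a month the medians run from 15 to 21 and from 10 to 17. Pr(stop) does not change.

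**The case for a change.** The strongest case is that two ordinary ways of counting can give opposite decisions on the same data. Suppose a patient arrives every 15.2 days and patients 3, 6 and 9 have events starting 3 days after dose 1. Patient 9 arrives on day 8 × 15.2 = 121.6, and the event is confirmed at 121.6 + 3 + 8 = 132.6. If events count when confirmed, the seventh evaluated patient is patient 9, and 3/7 (.979) stops the trial. In enrolment order, patients 1 to 7 are complete at 6 × 15.2 + 57 = 148.2 with 2/7 (.895). With no further event, 3/12 (.882) continues again.

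This holds if no look falls between 7 and 12. Table 7 supports that premise for the simulation: looking after every patient from the seventh gives Pr(stop) .379 at true rate .15, not .25. But the rule as written is the posterior criterion, and Section 10 does not forbid applying it between listed counts. In enrolment order, patients 1 to 9 are complete at 7 × 15.2 + 57 = 163.4, and 3/9 gives .950, which meets the criterion. The stop then comes 163.4 − 132.6 = about 31 days later, after two more arrivals (11 treated rather than 9). What stands is that the counting order can move an individual decision near a boundary.

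The large loss of protection comes only from counting everyone one week after dose 1. At that point nobody could have been evaluated for an event that must last longer than a week, so this reading conflicts with the plan's own definition. The event-first reading is plausible, but it stops more often and so errs toward caution.

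It is also argued that medians of 7 and 12 require enrolment to wait. They do if the column means patients treated and accrual is not very slow. The heading does not say treated, and step 3 shows that the values arise without any wait if it means evaluated.

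**Conclusion.** The omission is genuine: nothing in the document ties an observation window, a counting order or an enrolment pause to the toxicity rule. It is a gap that analysts would fill sensibly. The natural meaning of evaluated is that the patient's outcome is known. With that meaning, enrolment order and the eight listed counts, the boundaries are exact and Table 7's stopping probabilities are reproduced within simulation error, whatever window is used.

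The plausible departure, counting events once confirmed, adds about 5 to 6 percentage points to the chance of stopping at true rates .15 and .20. That assumes 2 patients a month and uniform onset; faster accrual or week-1 onset would widen it. The patient-number column could understate patients treated by about 5 at true rate .30 (17 against 12) and 6 at .40 (13 against 7). That requires the column to mean patients treated and enrolment not to pause, neither of which the document states.

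No boundary, sample size or stopping probability is shown to be wrong, and no particular window or counting order is shown to be better than the ordinary one. Writing the convention down would be harmless, but the soundness of the rule does not depend on it.

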If the previous infusion was completed without grade ≥ 3 infusion-associated AEs, the subsequent infusion of the first full dose of ofatumumab can start at a rate of 25 mL/hour and can be doubled every 30 minutes up to a maximum of 400 mL/h, according to Table 3.

Duration of the infusion will be approximately 4 hours if this schedule is followed. If the previous infusion was completed with grade ≥ 3 infusion-associated AEs, the subsequent infusion should start at a rate of 12 mL/hour according to Table 3.

Table 3. Infusion rate at subsequent Ofatumumab Infusion

Time	mL/hour
0 – 30 minutes	25
31 – 60 minutes	50
61 – 90 minutes	100
91 – 120 minutes	200
121+ minutes	400

During infusion the patient should be monitored closely and appropriate measurements should be performed whenever judged necessary.

There are no proposed or planned ofatumumab dose reductions for toxicities. Toxicities will be addressed by escalating premedication, slowing the infusion rate or delaying planned dose as determined by the treating physician.

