8.0 RESPONSE CRITERIA AND TOXICITY EVALUATION

Responses will be assessed according to the 2008 IWCLL guidelines (Table 5)⁷ at MDACC. Responses will be evaluated by physical examination; CBC; CT of chest, abdomen, pelvis; and for individuals in complete remission bone marrow aspirate and biopsy with evaluation of residual disease (MRD) by 4-color flow cytometry at least 3 months after completing ofatumumab.

Table 5. 2008 IWCLL Response Assessment

SITE	CR	PR
Nodes*†	None > 1.5 cm	Decrease ≥ 50%
Liver/Spleen	Not palpable	Decrease ≥ 50%
Symptoms	None	N/A
PMN	>1,500/µL	N/A
Platelet count	> 100,000/µL	>100,000/µL or increase ≥ 50% over baseline
Hemoglobin (untransfused)	>11.0 g/dL	>11.0 g/dL or increase ≥ 50% over baseline
Blood Lymphocytes	<4,000/µL	Decrease ≥ 50%
Bone Marrow Aspirate**	Normocellular <30% lymphocytes	> 50% decrease in marrow infiltrate or B lymphoid nodules
Biopsy	No lymphocyte infiltrate or nodules	

* CT scan of neck, chest, abdomen, and pelvis to confirm CR is recommended.

† Sum of the product of multiple lymph nodes.

** Evaluation for MRD will be performed either by 4-color flow cytometry or by molecular evaluation.

N/A=not applicable

Non-hematologic toxicity will be assessed, summarized and graded according to the Common Terminology Criteria for Adverse Events (CTCAE) Version 4.0. Hematologic toxicity will be assessed, summarized and graded according to the 2008 IWCLL Guidelines (Table 6).

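### Does the toxicity stopping rule lack a look schedule, so that Table 7 does not describe it?

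*Combined protocol and SAP*

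**What the plan says.** Section 10.0 (Statistical Considerations) puts a beta(1, 1) prior on the toxicity probability p and terminates the trial if the posterior probability that p exceeds 0.15 is at least 0.9. The next sentence turns this into counts. It opens "This rule will stop the trial if" and requires the ratio of patients with toxicity to patients evaluated to reach one of "3/7, 4/12, 5/17, 6/22, 7/27, 8/32, 9/37" or 10/42. Then: "The operating characteristics for toxicity are summarized in Table 7". That table is headed "Operating characteristics based on 1000 simulation study" and runs to the full 44 patients.

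The section gives no separate statement of a first look, a cohort size or a checking frequency. A countable event is an ofatumumab-related toxicity of CTCAE v4.0 grade 4 or higher "that persist longer than 1 week despite holding drug and/or dose reduction".

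**The concern.** The posterior criterion is written without restriction, so on its face it applies after any patient. The list names only eight sample sizes, and these are exactly the sizes at which the required count goes up by one. A list of change-points is also how one would write a continuous step boundary: three events stop the trial anywhere from 7 to 11 patients, four from 12 to 16, and so on. That reading agrees with the posterior sentence at every size from 7 onward, but it does not give Table 7.

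Two careful teams could therefore act differently. With 3 events in 11 patients the posterior is 0.908 and the criterion is met. If the next check is at 12 patients and no further event has occurred, 3/12 gives 0.882 and the trial continues. Table 7 is the plan's evidence that the rule protects patients without too many false stops, so it matters which rule it describes.

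Two wording points in the event definition can look like further inconsistencies. It mentions dose reduction, although Section 5.0 says "There are no proposed or planned ofatumumab dose reductions for toxicities". It also uses CTCAE grades, while Section 8.0 grades hematologic toxicity by IWCLL.

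**Working it through.** **Inputs (all from Section 10.0).** Prior beta(1, 1); threshold 0.15; cutoff 0.9; the eight listed ratios; maximum 44 patients; Table 7 from 1000 simulated trials.

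**Step 1: the boundaries.** With x events in n patients the posterior is Beta(1 + x, 1 + n − x). The table gives its probability above 0.15 at each listed count and at one event fewer.

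| n | listed x | posterior at x | posterior at x − 1 |
|---|---|---|---|
| 7 | 3 | 0.979 | 0.895 |
| 12 | 4 | 0.966 | 0.882 |
| 17 | 5 | 0.958 | 0.879 |
| 22 | 6 | 0.954 | 0.881 |
| 27 | 7 | 0.951 | 0.885 |
| 32 | 8 | 0.951 | 0.889 |
| 37 | 9 | 0.951 | 0.894 |
| 42 | 10 | 0.951 | 0.899 |

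Every listed count is the smallest that meets the criterion at its own n.

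**Step 2: reproduce Table 7.** The check is an exact forward recursion. Carry the binomial distribution of the event count patient by patient, remove the probability at or above the boundary at each look, and add up what was removed. The simulation standard error is √[P(1 − P)/1000], with P the exact value. At 15% with listed looks, √(0.229 × 0.771/1000) = 0.0133 and (0.25 − 0.229)/0.0133 ≈ 1.6.

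| True rate | Table 7 | Looks at 7, 12, …, 42 | Gap (SE) | After every patient from 7 | Gap (SE) |
|---|---|---|---|---|---|
| 0.05 | 0.004 | 0.006 | −0.7 | 0.019 | −3.4 |
| 0.10 | 0.07 | 0.060 | 1.4 | 0.135 | −6.0 |
| 0.15 | 0.25 | 0.229 | 1.6 | 0.379 | −8.4 |
| 0.20 | 0.49 | 0.501 | −0.7 | 0.660 | −11.4 |
| 0.30 | 0.89 | 0.912 | −2.5 | 0.959 | −10.9 |
| 0.40 | 0.99 | 0.995 | −2.5 | 0.998 | −7.0 |

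With the listed looks, the median and quartiles of patients treated are 12 (7, 22) at 30% and 7 (7, 12) at 40%, exactly as printed. At 20% the exact values are 42 (17, 44) against 44 (12, 44) in Table 7. That difference is borderline sampling noise: the exact stopping probability is 0.501, so the median sits on the edge between 42 and 44, and the probability of stopping by patient 12 is 0.243, so the lower quartile sits on the edge between 12 and 17.

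**Step 3: is the schedule pinned down by Table 7 alone?** Not quite. Looks at 7 to 37, leaving out 42, give 0.006/0.059/0.220/0.475/0.888/0.992, with a largest gap of 2.3 SE. The table therefore supports this family of looks, and the printed 10/42 supplies the last one.

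**Step 4: the unrestricted reading.** If the list is ignored altogether, the criterion is met at 1/1 (0.978), 1/2 (0.939) and 2/6 (0.926). Checking from patient 1 then stops 51% of trials at a true rate of 15% and 11.7% at 5%. Starting at patient 7 is an assumption that already borrows the first look from the list.

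**Step 5: what the difference would mean.** At a true rate of 30%, continuous checking from patient 7 would stop 95.9% of trials. Of all trials, the listed looks stop at the same patient in 35.3%, later in 55.9% (median delay 4 patients) and never in 4.7%. In return, false stops are fewer: 0.6% against 1.9% at a true rate of 5%, and 6.0% against 13.5% at 10%.

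**The case for a change.** The strongest case for a change is that a safety rule should be executable from its text alone. Here the sentence, the list and the table agree only once the reader restricts the sentence to the eight listed sizes, and the plan never writes that restriction. The step-boundary reading is not perverse, since the listed sizes are the change-points, and it moves stopping at a true rate of 15% from about 23% to about 38%. One clause would settle it.

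The ambiguity in wording stands, and so do the numbers. The inference that the rule has no schedule, or lacks the properties claimed for it, does not. The list is introduced as the way the rule stops the trial, its denominators are numbers of patients evaluated, and they run 7 and then every 5. An analyst who takes them as the evaluation points recovers both the boundaries and Table 7. The competing reading takes the first look from the list and disregards the other seven, and no section calls for patient-by-patient checking. The contrast between 3/11 and 3/12 is what happens under any rule with discrete looks.

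The wording points do not add to the case. Holding drug alone satisfies the event definition, so it does not conflict with Section 5.0, which allows a planned dose to be delayed. The definition is stated to be for safety monitoring and names its own grading scale. Section 8.0 governs how hematologic toxicity is assessed and summarized. A cross-reference is absent, but nothing contradicts.

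**Conclusion.** No change follows. The look schedule is implicit in the eight denominators. Under it every boundary is exact and all six Table 7 stopping probabilities are reproduced to within about 2.5 simulation standard errors, so no printed figure is wrong. Writing the looks out would record what the list already implies and would leave every number as it is. Moving to continuous checking would be a different design that the documents do not ask for. It would stop a median of 4 patients sooner in many trials with high toxicity, at the price of roughly doubling false stops at a true rate of 10% (13.5% against 6.0%).

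This rests on reading the listed ratios as evaluation points, which is the natural sense of the sentence and the one that Table 7 supports. If the investigators in fact meant to check after every patient, Table 7 would understate stopping by the amounts shown above, but nothing in the plan says so.
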